
However, it seems that at present these precautions are not able to reduce the incidence of the oxidative damage-related pathologies [25, 26].

Nonetheless, transfusions of red cell concentrates continue to be a life-saving therapy and they are fundamental to treat the anemia of preterm infants. Anemia in preterm infants, compared to the physiological anemia in full-term newborns, is characterized by a faster and more serious decline in the levels of hemoglobin (Hb) and hematocrit (Hct). The repeated venous samplings for laboratory tests, the lack of nutrients, the insufficient production of endogenous erythropoietin, associated to the concurrent infections and to the possible blood losses, further exacerbate the anemia of prematurity [27-32]. In spite of the numerous precautions, such as the increasingly reduced volumes of samplings, the reduction of transfusion limits and the widespread use of iron and erythropoietin, the transfusion of 20 ml/kg of red cell concentrates is inevitable in almost 90% of ELBW patients [30-32]. Since in ELBW preterm infants anemia is particularly relevant during the first weeks of life, they all receive most transfusions before the 32nd week of PMA [14-16, 25].

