Compared to the adult donor blood, cord blood taken from placenta and umbilical vessels has some important characteristics in terms of neonatal transfusions. As a matter of fact, cord red cells contain HbF, which is more physiological than HbA in preterm infants because of its higher affinity to oxygen. Moreover, the immune and infection profile of cord blood is absolutely “naïve”, as shown by the years of experience with hematopoietic transplants [33]. All these characteristics are a valid reason for using it when transfusing preterm infants. The use of autologous or allogeneic umbilical cord blood as an alternative to the transfusion of adult red cells was greatly confirmed by literature to the point that cord blood red cell concentrates were included by the Italian National Blood Center in the blood components acknowledged by the UNI 10529:1996 norm that regulates their traceability (umbilical cord blood red cell concentrates, UCB-RBC, blood component 73). These units can be irradiated like those obtained from adult donors. In a recent study, we tested the ability of the UNICATT Cord Blood Bank to cover the transfusion needs of low birth weight infants who were admitted to the Neonatal Intensive Care Unit (NICU) of our hospital with red cell concentrates from cord blood [46]. The study included patients who were born before the 30th week of gestation and/or with a birth weight lower than 1,500 g and who needed transfusions during the first 28 days of life. After the first transfusion event, each patient was assigned to the treatment arm (umbilical cord blood-packed red cells, UCB-RBC) or to the control arm (adult donor red cell concentrates, A-RBC), depending on the availability of UCB-RBC of the same blood type (ABO-Rh). From March, 1 to February, 28 2014, 20 patients out of the 63 that were hospitalized in the NICU were included in our study. Out of 20 infants, 9 were transfused with UCB-RBC and 11

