with A-RBC. Overall, we transfused 23 UCB-RBC units and 27 A-RBC units. We observed that the two types of blood components led to a similar increase in the hematocrit levels and that the patients that were transfused with UCB-RBC or A-RBC received a similar number of transfusions at similar time intervals. There were no adverse events nor transfusion reactions and no CMV infections were recorded. In this limited number of patients, with an average follow-up of 57 days, the incidence of prematurity-related pathologies appeared to be globally comparable [46]. However, it was interesting to notice that the only two patients who did not develop ROP were only transfused with UCB-RBC [47]. More recently, a prospective study was carried out to show that the incidence of ROP was related to the levels of HbF in patients: the lower the levels, the greater the incidence [13]. Among those patients, the level of HbF was obviously inversely proportional to that of HbA. Therefore, even if it was a limited number of patients, the absence of ROP among the patients who were transfused with umbilical cord blood indirectly confirms the potentially damaging effect of adult blood transfusions [46, 47]. Our feasibility study also demonstrated that with current resources we are able to cover 50% of these patients' transfusion needs [46].

At global level, the implementation of a program for the transfusion of cord blood in a preterm infant could have an important clinical impact. Additionally, the introduction of this transfusion strategy could be an advantage in the rationalization of resources when using blood components. Actually, according to the criteria of cellularity established by the Italian Bone Marrow Donor Registry (IBMDR), less than 10% of cord blood units are cryopreserved and listed for transplants [48].

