2. OBJECTIVES OF THE STUDY

The objective of the study is to investigate the correlation between the levels of HbF and the use of umbilical cord blood red cell concentrate transfusions in ELBW preterm infants and/or infants who were born before the 30th week of gestational age (GA). Since transfusions are one of the main mechanisms to reduce HbF, they will be carried out with umbilical cord blood red cell concentrates (UCB-RBC). Our objective is to demonstrate that UCB-RBC transfusions, until the 32nd week of PMA, guarantee average levels of HbF that are higher than in adult-RBC (A-RBC) transfusions. The following outcomes were defined:

Primary outcome:

- Average levels of HbF at 32nd week of PMA in patients receiving different transfusion support.

Secondary outcomes:

- To show that UCB-RBC transfusions are not less effective than A-RBC transfusions, as for the post-transfusion increase in the hematocrit and the interval between two transfusions.
- To show the association between average levels of HbF during the inpatient stay and comorbidities (ROP, BPD, NEC, PVL and IVH) or deaths occurred within 36 weeks of PMA.

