5.4 The collection of cord blood will be carried out in the birth centers that are part of the Cord Blood Bank, according to the procedures used by the Bank itself. The collected units will be adequately conserved at low temperatures (2-6°C) and fractionated within 24 hours. The units that are not eligible for transplant because of low cellularity (total nucleated cells <1,200 x 10⁶), with a volume >60 ml excluding the anticoagulant (CPD, Citrate, Phosphate, Dextrose), without clots and/or hemolysis, will be considered eligible for fractionation to obtain UCB-RBC. Eligible UCB units will be fractionated by an automatic blood component processing system (the UNICATT Cord Blood bankl will use Compomat[®] G4 by Fresenius HemoCare GmbH, D-61346, Bad Homburg, Germany). Red cell concentrates will be resuspended in a preservative solution containing adenosine, glucose and mannitol (SAGM, ratio red cell: SAGM = 2:1) and filtered with the filter Purecell[®] NEO Neonatal High Efficiency Leukocyte Reduction Filter (Pall, East Hills, NY, USA) to remove leukocytes. Blood cultures for bacteria and fungi will be set up. Only the units that tested microbiologically negative will be considered eligible for transfusion (blood cultures, molecular and serological tests for HCV, HBV, HIV and syphilis). UCB-RBC units will be stored at a temperature of 2-6°C for 14 days, in order to allow the γ -irradiation (¹³⁷Cs) when they are assigned to the patient.

5.5 Transfusion request. Units will be requested according to the procedures established by the Blood Transfusion Service, based on the current legislation and in accordance with the guidelines reported in Annex III. When a blood request arrives, the hematologist on duty at the Blood Transfusion Service will check if the patient's name is included among those enrolled in the study and the date of completion of the 32nd week of PMA; then he/ she will identify ABO-Rh(D) units to transfuse (UCB-RBC if available, otherwise A-RBC). The transfusion dose will be determined regardless of the type of blood component being used and will be established according to the criteria generally implemented in the NICU. The UCB-

RBC and A-RBC units will be transfused within six hours in order to reduce functional alterations of red cells and the risk of microbial contamination.

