6. STATISTICAL CONSIDERATIONS

6.1 Definition of analysis sets

- **Enrolled (E) set or Intent-to-treat (ITT) analysis.** It will comprise all the enrolled patients, regardless of the administration or not of RBC transfusions.
- **Treated (T) set.** This group will comprise all the patients who were at least administered one transfusion, regardless of the completion of the observation period (36th week of PMA). Excluded from this set are the enrolled patients who were not transfused.
- **Per-Protocol (PP) set.** This group will comprise all the transfused patients who completed the observation period (36th week of PMA) or who died after completing it.

6.2 Calculation of sample size. The main goal of the study is to correlate the average HbF levels to the type of transfusion (UCB-RBC or A-RBC). With a population of 25 patients that will be studied during the following 8 weeks and a mortality rate of 1.9 patients/month, we expect to have 196 weekly doses of HbF to correlate to 98 transfusions. The total expected number of transfusion from birth to the completion of the 36th week of PMA was calculated to be around four transfusions per patient, with an UCB-RBC:A-RBC ratio of 1:1. In fact, for those patients with birth-determined characteristics similar to those of the studied population, the average number of transfusions within the 36th week of PMA is around 4 transfusions/patient [25], while in our previous study the average number of transfusions was 3 ± 1.7 [46]. In accordance with the literary data, preterm infants have an expected HbF concentration between 85% and 90% at birth and between 70% and 75% at the 36th week of PMA [54]. We expect that for the newborns who will not be transfused the HbF levels will stay in this range (70%-90%), while for the patients who will be transfused with adult red cells, HbA will dilute HbF. Even though there are no literary data yet, if we know the volume of transfused red cells (20 ml/kg) and the patient's blood volume, we can also assume that, for every adult red cell transfusion, HbF will be reduced by 15-20% compared to the pre-transfusion values until reaching levels lower than 20% among those patients who were transfused more than 4 times with adult blood.

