6.3 Statistical data analysis. The continuous variables will be expressed as mean (\pm SD) or as median (interquartile ranges, IQR); all deviations from normality will be detected with the Shapiro-Wilk test. The categorical variables will be expressed as n, (%), percentage). HbF levels in different type of transfusions will be compared in univariate analysis Mann-Whitney U test, end Kruskall Wallis test). Similarly, the transfusion efficacy analysis will be carried out based on a UCB-RBC and A-RBC non-inferiority study design by comparing the average time interval between two subsequent transfusions and the average post-transfusion capillary Ht

increase (Δ Ht) (Mann-Whitney U Test). The transfusion sample included in the study makes it possible to detect a difference between groups that is equal to at least 1 standard deviation with type I error $\alpha = 0.05$ and type II error $\beta = 0.2$ and a medium effect size (0.6). The correlation between the type of transfusion and other variables (prematurity related pathologies) will be tested using Fisher's exact test. Secondarily, in order to evaluate the effect of HbF reduction on the onset of prematurity-related pathologies, the levels of HbF levels will be inserted in a multiple linear regression model, by expressing the correlation between the onset of prematurity-related pathologies and the variables in terms of odds ratios (ORs \pm 90% confidence interval).

6.4 The primary outcome analysis will be tested on "E", "T" and "PP" sets. Transfusion efficacy outcome will be tested on "T" and "PP" sets.

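### The HbF rank test in section 6.3 has no rule for infants given both products or none, and its power sentence does not describe a comparison of about 25 infants

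*Combined protocol and SAP*

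**What the plan says.** Section 2 defines the primary outcome per patient: "Average levels of HbF at 32nd week of PMA in patients receiving different transfusion support". Section 6.4 tests it on the E, T and PP sets. Under section 6.1, set E keeps enrolled infants who were never transfused; T and PP drop them.

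Section 5.5 selects the product each time a request arrives: "UCB-RBC if available, otherwise A-RBC". The feasibility study described in the Introduction worked differently: "After the first transfusion event, each patient was assigned to the treatment arm". The present plan has no such rule.

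Section 6.2 works with 25 infants, 196 weekly HbF values and 98 transfusions. The expected number of transfusions to 36 weeks PMA "was calculated to be around four transfusions per patient, with an UCB-RBC:A-RBC ratio of 1:1".

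The only test that section 6.3 names for HbF is this: "HbF levels in different type of transfusions will be compared in univariate analysis Mann-Whitney U test, end Kruskall Wallis test". The one regression in the plan is secondary and models prematurity-related pathologies. After the sentence on transfusion efficacy, section 6.3 states that the transfusion sample can detect a difference of at least 1 SD with alpha 0.05 and beta 0.2, and in the same sentence gives an effect size of 0.6.

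**The concern.** A rank test needs every infant in exactly one group. With the product chosen at each request, an infant can be UCB-only, A-only or mixed, and in set E also untransfused. Naming Kruskal-Wallis hints at more than two groups, but none is defined. The primary test therefore cannot be run without a further decision, and nothing stops that decision being made after HbF has been seen.

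The choice is not neutral. Infants with few transfusions are more often single-product, so any grouping that separates mixed infants, or pools them with one product, also sorts infants by number of transfusions.

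The unit of analysis is also unsettled. Sections 2, 6.1 and 6.4 speak of patients, while 6.2 and the power sentence in 6.3 count transfusions. At stake are the size and credibility of the primary result and whether its power has been stated at all.

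**Working it through.** **1. The plan's power figure.** For two groups, two-sided alpha 0.05 and 80% power, n per group ≈ 2(1.96 + 0.84)²/d².
- d = 0.6: 44 by the normal formula, 45 by t test, 47 for Mann-Whitney (relative efficiency 0.955).
- d = 1: 16, 17 and 18.
- 98 transfusions at 1:1 are 49 against 49. If independent, power at 0.6 SD is 84% (t) or 82% (Mann-Whitney), close to the stated 80%. At 1 SD it is 99.8%.

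So 0.6 SD fits about 98 independent transfusions, and the two effect sizes cannot both correspond to 80% power.

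**2. The same calculation with infants.** The best case is two clean groups, 12 against 13.
- 0.6 SD: 30% (t), 27-29% (Mann-Whitney).
- 1 SD: 67% (t), 63-65% (Mann-Whitney).
- Detectable with 80% power: about 1.2 SD (1.17 by t).

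**3. How many infants are mixed.** If each of m units is independently 50:50, P(both products) = 1 − 2 × 0.5^m: 50%, 75% and 87.5% for m = 2, 3 and 4. The mean by 32 weeks is not given. Four is the figure to 36 weeks, and the Introduction says of ELBW infants that "they all receive most transfusions before the 32nd week of PMA". In the feasibility study, "Overall, we transfused 23 UCB-RBC units and 27 A-RBC units", that is 50 units in 20 infants, or 2.5 each. I take 3 as the central value. The documents give no within-infant correlation of product, so I use 0, 0.3 and 0.6 (beta-binomial). At mean 3, about 15, 11 and 6 of 25 infants are mixed.

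**4. What the grouping does to the result.** Inputs:
- Adult unit: 17.5% relative loss, the middle of section 6.2's figure ("for every adult red cell transfusion, HbF will be reduced by 15-20% compared to the pre-transfusion values").
- Cord unit: 3% loss, an assumption. With cord HbF about 72.5% and recipient HbF 87.5%, 0.175 × (87.5 − 72.5)/87.5 = 0.03.
- Units per infant: at least one, mean 3, SD 1.7 (the spread in section 6.2).
- Starting HbF mean 87.5, SD 3; noise SD 5 (assumptions).
- A comparison with fewer than two infants in a group counts as no rejection.

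Results at correlation 0 / 0.3 / 0.6, with simulation error of a few percentage points:

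| Grouping | Difference (points) | Power |
|---|---|---|
| Any-UCB vs A-only | about 2 / 10 / 17 | 3% / 25% / 73% |
| UCB-only vs any-A | 23-25 | 96-100% |
| Kruskal-Wallis: UCB-only, mixed, A-only | – | 88-99% |

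**5. No product difference (3% loss for both).** The three-group Kruskal-Wallis test rejects in about 26%, 16% and 10% of trials, against a nominal 5%. The two pooled two-group comparisons show spurious gaps of about 1 to 4 points in opposite directions. Number of transfusions is the only thing separating the groups. UCB-only against A-only does not lean, but it discards the mixed infants.

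**6. If the transfusion is the unit.** With four transfusions in each of 25 infants, treating all values as independent gives a Mann-Whitney type I error of 5% at product correlation 0, 8-12% at 0.3 and 10-21% at 0.6 (assumed intraclass correlation 0.3-0.8).

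**The case against.** **Kruskal-Wallis is the natural reading and is not weak.** This stands as to power: three groups keep 88-99% at mean 3. It does not rescue the plan, because the groups are not written down and the test is confounded by number of transfusions.

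**The swing is partly the assumed correlation.** This stands. A reader might infer that grouping alone moves the result from 2 to 25 points. At a fixed correlation of 0.6 the contrast is about 17 against 25 points and 73% against nearly 100%. The extreme contrast needs correlation 0, and matching units on ABO-Rh makes some positive correlation likely.

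**The sentence may concern the endpoint in section 3.5, HbF before and after each transfusion.** That is possible, and mixed infants would then need no group. But repeated values within an infant would be treated as independent, and the per-patient primary outcome would have no test of its own.

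**The power sentence may cover only transfusion efficacy.** Its position and its reference to transfusions support this. The primary outcome then has no power statement, and the two effect sizes still conflict.

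**1 SD can be made to fit 25 infants.** A one-sided normal approximation gives 80.4%. The plan states no sidedness, and with Mann-Whitney the figure falls to 76%.

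**Conclusion.** The point holds, in bounded form. The missing group rule and the unsettled unit follow from the text and need no simulation. The incompatible effect sizes follow from a standard calculation: 45 against 17 per group. The sizes in steps 4 to 6 rest on assumed unit counts, product correlation, cord loss and noise, and should be read as ranges.

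Three stronger readings are not supported:
- *That grouping could turn a benefit into a harm.* Significant results in opposite directions within one dataset occurred in at most 0.5% of simulated trials under the plan-like effect and 1.1% with no product difference.
- *That the study must fail for lack of power.* The plan gives no SD for HbF and expects large falls after adult units, so 30% at 0.6 SD says nothing against a much larger true effect.
- *That gestational age or baseline HbF biases the comparison.* The only confounder demonstrated is number of transfusions; adjustment for the other two is a safeguard and a gain in precision.

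**What to change.** In section 6.3:
- Name the infant as the unit for the primary outcome.
- Make the primary analysis a regression of 32-week HbF on the numbers of A-RBC and UCB-RBC transfusions received before that measurement, adjusted for gestational age and pre-transfusion HbF. Test the difference between the two coefficients. Mixed infants then contribute fully, and untransfused infants enter with zeros.
- Pre-specify one outcome scale. Section 6.2 does not settle whether the loss per adult unit is relative or in points. Five relative losses of 15-20% leave 85 × 0.80⁵ = 27.9 to 90 × 0.85⁵ = 39.9, above the stated level of under 20%. Five 15-point losses leave 10-15, but five 20-point losses go below zero. The plan sets no ceiling on the number of transfusions, and seven 20% relative losses from 85 do reach 17.8.
- Keep the rank tests as descriptive, with UCB-only, mixed, A-only and untransfused groups defined.
- Use an infant random effect for transfusion-level outcomes and repeated HbF values.

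In sections 6.2-6.3, restate power with one effect size for the number of infants expected to have a 32-week value.

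Cost: new text only. Date, number, type and volume of transfusions, gestational age and HbF are already recorded (sections 5.6-5.9). The downsides are a linear dose assumption in about 21-25 infants, an effect per unit that conditions on the transfusions received, and a less favourable power figure.

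### Section 6.3 claims a non-inferiority design for transfusion efficacy but names only a Mann-Whitney test, with no margin or confidence-limit rule; if the two products perform alike, that analysis cannot support the claim.

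*Combined protocol and SAP*

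**What the plan says.** Section 2 (Objectives of the study) lists as a secondary outcome: "To show that UCB-RBC transfusions are not less effective than A-RBC transfusions, as for the post-transfusion increase in the hematocrit", and likewise for the interval between two transfusions.

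Section 6.3 (Statistical data analysis) describes the corresponding analysis as a UCB-RBC and A-RBC "non-inferiority study design by comparing the average time interval between two subsequent transfusions and the average post-transfusion capillary Ht" increase, followed in brackets by the Mann-Whitney U test. The sentence opens by likening this analysis to the HbF comparison before it, which is an ordinary test between groups.

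The next sentence says the transfusion sample "makes it possible to detect a difference between groups that is equal to at least 1 standard deviation", at alpha 0.05 and beta 0.2, and also cites an effect size of 0.6.

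Section 6.4 states: "Transfusion efficacy outcome will be tested on" the T (treated) and PP (per-protocol) sets. It gives no rule for declaring success. Section 3.5 defines the two endpoints without an acceptable loss. The only confidence interval in the plan, at 90%, is for the odds ratios of prematurity-related pathologies.

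**The concern.** Showing that one product is not worse than another requires a stated largest acceptable loss and evidence that the true loss is smaller. An ordinary Mann-Whitney test asks only whether the groups differ. A significant result favouring UCB-RBC would imply non-inferiority; a non-significant result would not, because it may simply reflect too few data.

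The non-significant case is the one to expect. The Introduction reports from the earlier study that "the two types of blood components led to a similar increase in the hematocrit levels" and that transfusion intervals were similar too. The plan does not say how such a result will be read. If it were read as success, a real loss of transfusion efficacy could pass, and the smaller the sample, the more easily it would pass.

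**Working it through.** **Inputs from the documents.** Section 6.2: 98 transfusions, about four per infant, split 1:1, so 49 per type. Dividing, 98/4 = 24.5 infants (the planned number is 25). Each infant's transfusions yield one fewer interval, so 98 − 24.5 = 73.5 intervals, or about 37 per type. Section 6.2 also says "in our previous study the average number of transfusions was 3", which gives 3 × 24.5 = 73.5 transfusions (36.75 per type) and 73.5 − 24.5 = 49 intervals (24.5 per type). Section 6.3: alpha 0.05, sidedness not stated.

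**Assumptions not in the documents.** Two-sided 0.05 unless noted; normal data; independent transfusions; intervals split equally and each counted under the product that opens it; effects in SD units, because no SD is given for either endpoint.

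**Step 1. The plan's own power figure.** Power = Φ(d/√(2/n) − 1.96). With d = 0.6 and n = 49: Φ(2.970 − 1.96) = 0.844. With the Mann-Whitney efficiency of 0.955 it is 0.827. The stated 80% is therefore supported for 0.6 SD. It does not match 1 SD, for which power is above 99.8% and only 16 to 17 per type would be needed. Both figures describe a difference to detect; neither is called an acceptable loss.

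**Step 2. What the named test delivers if the products are equal.** UCB-RBC comes out significantly better in 0.05/2 = 2.5% of trials (2.4% in 20,000 simulated trials at 49 per type). In all other trials the test gives no support for the objective.

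**Step 3. What would pass if p>0.05 were read as non-inferiority.** This is an illustration; the plan does not state that reading. With s = d√(0.955/(1/n₁ + 1/n₂)), the chance of p>0.05 is Φ(1.96 − s) − Φ(−1.96 − s). For d = 0.5 and n = 49 per type, s = 2.419 and the chance is 0.323.

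| Endpoint | n per type | True deficit 0.5 SD | True deficit 0.6 SD |
|---|---|---|---|
| Haematocrit rise, 4 per infant | 49 / 49 | 32% | 17% |
| Same, split as the earlier study's 23:27 units | 45 / 53 | 33% | 18% |
| Interval, 4 per infant | 37 / 37 | 44% | 29% |
| Haematocrit rise, 3 per infant | 36.75 each | 45% | 29% |
| Interval, 3 per infant | 24.5 each | 60% | 46% |

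At one-sided 0.05, Φ(1.645 − s), the first row becomes 22% and 10%, and the third 32% and 19%. Simulated Mann-Whitney tests agree closely: 33% and 18% at 49 per type, 47% and 31% at 37.

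**Step 4. What a margin-based rule could achieve.** Power with no true difference = Φ(m/√(2·DE/n) − 1.96), for margin m and a two-sided 95% interval on the mean difference. DE is 1 if transfusions are independent, 1 + (k − 1)·ICC if each infant receives only one product, and 1 − ICC if infants receive both equally and are compared within infant. For haematocrit rise n = 49 and k = 4; for the interval n = 36.75 and k = 3. Assumed ICC: 0.1 to 0.5.

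| Assumed margin and setting | Haematocrit rise | Interval |
|---|---|---|
| 0.6 SD, independent | 84% | 73% |
| 0.6 SD, one product per infant | 74% to 47% | 65% to 44% |
| 0.6 SD, both products, within infant | 88% to 99% | 77% to 95% |
| 0.4 SD, independent | 51% | 40% |

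The formula runs slightly high. Simulation with t intervals (24 infants, four transfusions each) gave 70% to 43% and 85% to 98% for haematocrit rise in the second and third rows. Section 5.5 chooses the product at each request ("UCB-RBC if available, otherwise A-RBC"), so a mix within infants is likely.

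**Step 5. Could 1 SD serve as the margin?** With m = 1 and n = 49, a true deficit of 0.5 SD would pass with probability Φ((1 − 0.5)/√(2/49) − 1.96) = 0.70, and one of 0.6 SD with probability 0.51. It would give little protection.

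**The case against.** The strongest reply is that section 6.3 states no null hypothesis. A Mann-Whitney test on margin-shifted data, or a Hodges-Lehmann confidence limit, is a valid non-inferiority method, so the defect may be an unspecified margin rather than a wrong test. It is true that the procedure could be made valid. But both versions need a margin and the plan has none. The link to the preceding HbF comparison and the power sentence about detecting a difference also point to an ordinary test.

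Second, the percentages in step 3 depend on a reading of p>0.05 that the plan never states, and on independence. That is correct, and they are offered only as an illustration. With clustering (ICC 0.1 to 0.5), simulation puts the 17% figure at about 21% to 26% if each infant receives one product and 16% to 11% if infants receive both equally.

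Third, a 95% interval is a choice. Alpha 0.05 without sidedness is compatible with a one-sided 0.05 test, that is, a two-sided 90% interval. At a 0.6 SD margin with independence, power would then be 91% for haematocrit rise and 82% for the interval. The level should be stated openly; the need for a margin is unchanged.

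Finally, this is one secondary outcome in a small, non-randomized, single-centre study. That limits the severity, but a small sample makes a non-significant result easier to obtain, not more informative.

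**Conclusion.** The concern holds. As written, the analysis can support the non-inferiority objective only if UCB-RBC proves significantly better, about a 2.5% chance if the products are equal. In the result the earlier study leads one to expect, it supports no conclusion. That rests on the text alone: no section gives a margin, a shifted null hypothesis, a confidence-limit rule or a reading of p>0.05. The 32% and 17% (haematocrit rise) and 44% and 29% (interval) rest on the further assumptions listed in the working and on a misreading the plan does not commit to. This should be fixed before analysis; the primary HbF comparison is not affected.

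**What to change.** In section 6.3, for each of the two endpoints, add wording such as:

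> The difference UCB-RBC minus A-RBC will be estimated with a two-sided 95% confidence interval that allows for repeated transfusions per infant. Non-inferiority will be claimed only if the lower limit lies above minus the margin in both the T and PP sets. The margin is a positive number, fixed and justified before the data are opened.

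If a 90% interval is preferred, say so and give the reason. State margins in haematocrit points and in units of time, justified as acceptable losses, and not borrowed from the 1 SD or 0.6 in the power sentence.

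If no margin can be agreed, replace non-inferiority by comparison in section 6.3, reword the section 2 outcome as estimating the difference with its confidence interval, and state that p>0.05 will not be read as equal efficacy.

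The cost is text plus one justified margin per endpoint, or text alone if the claim is dropped; no extra infants or blood samples are needed. The downside is that the claim may not be reached: power is moderate at a 0.6 SD margin and about even or worse at 0.4 SD under independence, and requiring success in both sets lowers it slightly.

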4. TEST POPULATION

The study will include preterm infants who met the criteria of inclusion/exclusion and whose parents/tutors have given their informed consent. Based on the number of patients hospitalized every year in our NICU (roughly 150 patients/year) and the characteristics of the test population, we expect to achieve the sample size of 25 patients in 10 months.

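### Section 6.3 gives one transfusion sample two incompatible detectable effects (1 SD and 0.6), and no detectable difference is stated per infant for the primary outcome

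*Combined protocol and SAP*

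**What the plan says.** - **Power (section 6.3).** One sentence covers what the text calls the transfusion sample. It "makes it possible to detect a difference between groups that is equal to at least 1 standard deviation" with alpha 0.05 and beta 0.2, "and a medium effect size (0.6" in brackets. It does not state sidedness or name the variable.
- **Analyses (section 6.3).** "HbF levels in different type of transfusions will be compared in univariate analysis Mann-Whitney U test", with Kruskal-Wallis named alongside. Immediately before the power sentence, "the transfusion efficacy analysis will be carried out based on a UCB-RBC and A-RBC non-inferiority study design"; no margin is given.
- **Size (sections 4 and 6.2).** "we expect to achieve the sample size of 25 patients in 10 months". From these infants "we expect to have 196 weekly doses of HbF to correlate to 98 transfusions", at "around four transfusions per patient, with an UCB-RBC:A-RBC ratio of 1:1".
- **Primary outcome (section 2).** "Average levels of HbF at 32nd week of PMA in patients receiving different transfusion support". Section 6.4 tests it on the E, T and PP sets, and section 6.1 lets the E set include infants who were never transfused.
- **Product received (section 5.5).** The choice is made at each request: cord product when available, adult product otherwise. One infant can therefore receive both.

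**The concern.** In SD units, one sample with one alpha and one beta has a single detectable effect. The sentence gives two, and the larger is 1/0.6 = 1.67 times the smaller. A reader cannot tell which figure applies, to which analysis, or to which unit.

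The unit matters because the sentence counts transfusions while the primary outcome is defined in patients. A claim of 0.6 based on 98 transfusions says little about a comparison with at most 25 units. If it is left in place, a null result could later be defended with a sensitivity that the design has only if transfusions within an infant are unrelated.

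**Working it through.** **Inputs.** 98 transfusions at 1:1, so 49 vs 49 (section 6.2); 25 infants (section 4); alpha 0.05 and power 80% (section 6.3). Two assumptions are mine. Sidedness is not stated, so both versions are shown. No split of infants is given, so 12 vs 13 is used as the most sensitive two-group split.

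**Method.** For the t-test, power comes from the noncentral t distribution with n1 + n2 − 2 degrees of freedom and noncentrality d × √(n1·n2/(n1+n2)). Mann-Whitney power was simulated on normal data, with the exact test for the infant-level figures.

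**Step 1. The plan's figures at transfusion level, taken as independent.** √(49×49/98) = 4.95.
- Two-sided, 80% power is reached at 0.57 SD (t-test) or 0.59 SD (Mann-Whitney). One-sided, the t-test gives 0.51 SD.
- At 0.6, two-sided power is 84% (t-test) or 82% (Mann-Whitney). The 0.6 is therefore reproduced.
- At 1 SD, two-sided power by t-test is 99.8%, not 80%. Detecting 1 SD needs only 17 per group two-sided, or 14 one-sided (t-test). The 1 SD is not reproduced for this sample on either sidedness.

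**Step 2. Infant level, 12 vs 13.** √(12×13/25) = 2.50.

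| | t-test | Mann-Whitney |
|---|---|---|
| Detectable at 80% power, two-sided | 1.17 SD | 1.22 SD |
| Detectable at 80% power, one-sided | 1.03 SD | about 1.07 SD |
| Power at 1 SD, two-sided | 67% | 63% |
| Power at 1 SD, one-sided | 78% | 76% |
| Power at 0.6 SD, two-sided | 30% | 27% |

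Two-sided, neither printed figure fits. One-sided, 1 SD comes close.

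**Step 3. A possible origin of the 1 SD.** The one-sided normal formula at d = 1 gives 2 × (1.645 + 0.842)² = 12.4 per group, or about 25 in total. This equals the planned number of infants.

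**Step 4. What independence is worth.** There are 98/25 = 3.92 transfusions per infant. With design effect 1 + (3.92 − 1) × ICC and a two-sided t-test:

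| Assumed ICC | Design effect | Effective transfusions | Detectable |
|---|---|---|---|
| 0 | 1.00 | 98.0 | 0.57 SD |
| 0.1 | 1.29 | 75.9 | 0.65 SD |
| 0.3 | 1.88 | 52.2 | 0.79 SD |
| 0.5 | 2.46 | 39.8 | 0.91 SD |
| 1 | 3.92 | 25.0 | 1.17 SD |

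The plan gives no ICC, so these values are illustrative. The formula treats each infant as receiving a single product; mixing of products would change the loss. Section 6.3 names no method for repeated transfusions in one infant.

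**Step 5. Are there two infant groups?** If each of four transfusions were an independent 50:50 draw (an assumption), 25 × (1 − 2 × 0.5⁴) = 21.9 infants would receive both products and about 1.6 would receive each product alone. So 12 vs 13 is a limit on sensitivity, not a description of the expected data.

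**The case against.** **The sentence may merge two sound calculations.** The objective in section 2 is directional, and Step 3 shows that a one-sided normal formula at 1 SD returns 25. On this reading 1 SD belongs to the infants and 0.6 to the transfusions. That is plausible, and it means the 1 SD should not be called baseless. It does not rescue the text, which attaches both figures to transfusions and states no sidedness. Even one-sided, the planned Mann-Whitney test has about 76% power at 1 SD.

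**The sentence may be meant to cover HbF as well.** Section 6.2 sizes the main goal in HbF values and transfusions, and section 6.3 introduces the efficacy analysis as similar to the HbF analysis. If so, the primary outcome is not without any power statement; the statement is in the wrong unit. What stands is that no detectable difference is given per infant.

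**A two-group figure may not describe the primary analysis.** Kruskal-Wallis implies three or more groups, and the E set can hold untransfused infants. This is correct. It is why the grouping must be defined first and 12 vs 13 given only as a bound.

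**The expected separation is large.** Section 6.2 expects HbF of 70–90% without transfusion, and below 20% after more than four adult transfusions. A reader might infer from 1.17–1.22 SD that 25 infants are too few. The documents do not support that: they give no SD for HbF, so the expected separation cannot be put in SD units.

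**Conclusion.** The point holds as a fault in the power statement. One sentence gives 1 SD and 0.6 for the same sample at the same error rates, and both cannot be right. Only 0.6 fits 98 transfusions (0.57–0.59 SD two-sided), and only if the roughly four transfusions per infant are independent. For the primary outcome, any two-group comparison of 25 infants detects at best 1.17 SD (t-test) or 1.22 SD (Mann-Whitney) two-sided, and 1.03 or about 1.07 SD one-sided. These infant-level figures assume normal data, no losses and a near-even split.

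Neither printed figure is the power of the non-inferiority analysis, because that power depends on a margin and none is stated. A shortage of infants is not shown. The statement should be corrected, but this alone gives no reason to change the sample size.

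**What to change.** Replace the power sentence in section 6.3 with one statement per analysis, each naming the unit, the test and whether it is one- or two-sided.

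1. **Transfusion level.** State that 49 vs 49 transfusions give 80% power at 0.57 SD (t-test) or 0.59 SD (Mann-Whitney), two-sided, only if transfusions are independent. Add a figure that allows for clustering within infants, with the assumed ICC and the assumed mixing of products stated.
2. **Primary outcome.** First define how infants are grouped (cord only, adult only, both, none), consistently with the Kruskal-Wallis test and the E, T and PP sets. Then give the detectable difference for those groups. Quote 12 vs 13 only as the upper bound on sensitivity for a two-group comparison of 25 infants: 1.17 SD (t-test) and 1.22 SD (Mann-Whitney) two-sided; 1.03 SD and about 1.07 SD one-sided.
3. **Unsupported claims.** Remove 1 SD and 0.6 wherever they do not hold. If 1 SD was calculated for infants, say so, with its sidedness and test. Present neither figure as the power of the non-inferiority analysis.

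**Cost.** Rewording of section 6.3, a grouping rule and a stated ICC assumption. It needs no extra infants, samples or visits. The plan gives up an unqualified 0.6, and its stated two-sided sensitivity for the primary outcome becomes a difference larger than 1 SD.
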